### **5.6.2. Measurement of Compliance**

Compliance with protocol-defined investigational product is to be calculated by treatment group and combined REGN5069 as follows:

- (Number of actual infusions of study drug during the exposure period) / (Number of planned infusions of study drug during the exposure period on or before the time that the patient discontinues from the treatment phase of the study) x 100%

Treatment compliance is to be presented by descriptive statistics as well as the number (percentage) of patients who have 1, 2, 3 infusions.

### **5.6.3. Protocol Deviations**

All important and minor protocol deviations have been collected and reviewed on an ongoing basis throughout the study as described in the protocol deviation plan.

Protocol deviations are to be summarized for patients incurring any important deviation by count and percentage, and patients incurring each type of important deviation by count and percentage for FAS.

A patient listing of all important and minor protocol deviations is to be provided.

## **5.7. Statistical Methods for Efficacy**

Unless stated otherwise, all efficacy analyses are to be based on the FAS. Confidence intervals are to be constructed with level of confidence equal to 95%. With the exception of analyses based on the PPS, models including stratifying variables are to utilize the value of these variables as captured in the IWRS system. Analyses based on the PPS are to utilize the value of these variables as captured in the EDC system.

If no more than 10% of patients are available in a stratification cell, that stratification factor will not be used.

### **5.7.1. Primary Efficacy Analysis**

The primary efficacy endpoint is change from baseline to week 12 in the WOMAC pain subscale score.

The null hypotheses of no treatment difference between a REGN5069 dose and placebo against an alternative hypothesis of some treatment difference in change from baseline to week 12 in WOMAC pain subscale, physical function subscale, and Patient Global Assessment scores are to be tested for each dose. Multiplicity adjustment for the 6 null hypotheses are to be made using sequentially rejective multiple test procedure to control Type I error rate at 2-sided 0.05 level in the following order:

- H1: No treatment difference between 1000 mg REGN5069 and placebo groups in change from baseline to week 12 in WOMAC pain subscale score
- H2: No treatment difference between 100 mg REGN5069 and placebo groups in change from baseline to week 12 in WOMAC pain subscale score
- H3: No treatment difference between 1000 mg REGN5069 and placebo groups in change from baseline to week 12 in WOMAC physical function subscale score
- H4: No treatment difference between 100 mg REGN5069 and placebo groups in change from baseline to week 12 in WOMAC physical function subscale score
- H5: No treatment difference between 1000 mg REGN5069 and placebo groups in change from baseline to week 12 in Patient Global Assessment score
- H6: No treatment difference between 100 mg REGN5069 and placebo groups in change from baseline to week 12 in Patient Global Assessment score

If at any step a null hypothesis is not rejected, the testing is to stop and no further hypothesis in the order are to be tested.

The primary estimand for the primary objective is the difference in means between REGN5069 dose + protocol-defined rescue medication and placebo + protocol-defined rescue medication in the change from baseline to week 12 in the WOMAC pain subscale score of patients in the FAS. All collected data are to be included in the analysis regardless of whether prohibited medication was taken.

The above primary and secondary efficacy variables are to be analyzed using a multiple imputation approach with a mixed-effect model for repeated measures (MMRM) based on the FAS.

Intermittently missing WOMAC subscale scores prior to treatment discontinuation are first to be imputed using the Markov Chain Monte Carlo method, and then the remaining missing data with a monotone missing pattern are to be imputed with a regression method. For patients who discontinued treatment due to reasons other than lack of efficacy, death or AEs, (reasons including discontinuation because of public health measures implemented in response to COVID-19, see Section 9 for details on the CRF implemented for collecting this information), their missing WOMAC subscale scores after discontinuation will be imputed under the missing-at-random assumption using the regression method with adjustment for covariates including treatment group, randomization strata (K-L category [2 to 3, or 4]), and baseline WOMAC subscale score. For patients who permanently discontinue treatment due to lack of efficacy, death or AEs, each imputed value obtained through the above method will be further adjusted by subtracting the mean change from baseline to the respective post-baseline time point calculated from patients in the same treatment group with observed data at that time point.

Missing data up to week 12 will be imputed 50 times to generate 50 complete data sets by using the SAS procedure PROC MI following the steps below:

- Step 1: The monotone missing pattern is induced by Markov Chain Monte Carlo (MCMC) method in MI procedure using seed number 1849. Any score imputed outside the range of the WOMAC subscale score of 0-10 is to be truncated to the nearest permissible value on the WOMAC scale according to the following algorithm:
  - If the imputed score > 10, then the final imputed score will be 10.
  - If the imputed score < 0, then the final imputed score will be 0.
- Step 2: The missing data at visits subsequent to treatment discontinuation are to be imputed using the regression method for the monotone pattern with seed number 1849 and adjustment for covariates including treatment groups, randomization strata (K-L category of index knee at screening, 2-3 or 4), WOMAC score at baseline and all values at preceding visits. Scores that are imputed outside the range of the WOMAC subscale will be truncated in the same manner as in step 1. As the regression method imputes missing data sequentially by visits, the truncation will be implemented after each visit iteration, during the MI procedure.

- Step 3: For patients who permanently discontinued study treatment due to lack of efficacy, death or AEs, the initially missing and now imputed WOMAC subscale scores at visits subsequent to treatment discontinuation are to be adjusted to be centered at the mean baseline value for that treatment group, i.e.:

imputed score = initial imputed score under MAR – (mean change from baseline subscale score at the post-baseline time point for the treatment group based on patients on treatment with non-missing data at that time point).

Scores that are adjusted to outside the range of the WOMAC subscale will be truncated following the same algorithm as in step 1.

Each imputed data set is to be analyzed using a MMRM with terms for baseline WOMAC Pain subscale score, randomization strata (K-L category [2 to 3, or 4]), treatment, visit, and treatment-by-visit interaction as fixed effects. The MMRM is to be fitted using the MIXED procedure in Statistical Analysis System (SAS) with an unstructured covariance matrix to model the within-patient errors. The denominator degrees of freedom is to be estimated using Kenward-Roger's approximation. In the event a model cannot be fit due to the estimation algorithm failing to converge, the covariance matrix for within-patient errors is to be modeled by an autoregressive 1 structure, followed by a compound symmetry structure if convergence is still not achieved for the prior.

The results from the 50 analyses are combined using Rubin's formulae (PROC MIANALYZE). The least squares means estimates for the mean change from baseline to week 12, as well as the difference of the estimates between REGN5069 each dose and placebo, with the corresponding standard error, p-value and associated 95% confidence interval are to be provided. Similar estimates at other visits are also to be presented.

The hypothesis for  $H_1$  is to be rejected when the p-value corresponding to the difference in change from baseline to week 12 between 1000 mg REGN5069 and placebo groups is less than 0.05 in WOMAC pain subscale score.

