**Figure 1: Study Flow Diagram**

a - Study drug will be administered every 4 weeks throughout the 12-week treatment period. Thus, study drug will be administered at the day 1 (baseline) visit and at the week 4 and week 8 visits.

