#### 10.4.3. Efficacy Analyses

##### 10.4.3.1. Primary Efficacy Analysis

The primary estimand for the primary objective is the difference in means between both REGN5069 dose + protocol-defined rescue medication and placebo + protocol-defined rescue medication in the change from baseline to week 12 in the WOMAC pain subscale score of patients in the FAS. All collected data will be included in the analysis regardless of whether prohibited medication was taken. Missing values will be imputed with the multiple imputation

approach, where intermediate missing data will be first imputed using the Markov Chain Monte Carlo method and then the remaining missing data with a monotone missing pattern will be imputed with a regression method. The regression model will adjust for treatment, randomization strata, and baseline score. For patients who drop out due to lack of efficacy or AEs, each imputed value will be further adjusted by subtracting the mean change from baseline to the respective post-baseline time point calculated from patients in the same treatment group with observed data at that time point. For each complete dataset, the primary efficacy endpoint of change from baseline to week 12 in WOMAC pain subscale score will be analyzed using analysis of covariance (ANCOVA) model which will include treatment, randomization strata, and baseline score as covariate. The least-squares means estimates, as well as the difference of the estimates between each dose and placebo with standard error, p-values, and 95% confidence intervals will be provided by combining results from the analyses of the multiple imputed datasets using Rubin's formulae. Further details will be provided in the SAP.

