### **5.5. Patient Disposition**

The analysis population is based on the FAS.

The end of study is defined as the date when the last patient completes the last phone call, withdraws from the study, or is lost to follow up (ie, the patient can no longer be contacted by the investigator).

Dose modification for an individual patient is not allowed.

Patients who permanently discontinue from study drug and who do not withdraw from the study are asked to return to the clinic for all remaining study visits and to participate in all study phone calls per the visit schedule.

Patients who permanently discontinue from study drug and who opt to withdraw from the study are asked to complete study assessments as follows:

- Patients who are withdrawn from the study before the primary endpoint visit (week 12) are asked to return to the clinic for 2 visits: once for an early termination visit consisting of the early termination assessments described in [Table 3](#) and again at the primary endpoint visit (week 12).
- Patients who are withdrawn from the study after the primary endpoint visit are asked to return to the clinic for early termination assessments, only.

The disposition of patients in the study are to be summarized by treatment group, combined REGN5069 and overall for FAS.

Percentages are to be calculated using the number of screened patients as the denominator for:

- Screened patients (defined as having signed the ICF).
- Screen Fail patients. Reason for screen failure is to be provided.
- Patients treated but not randomized (if applicable)
- Patients randomized (defined as having received a randomization number per IWRS). This row is to reflect grouping based on randomization assignment.
- Patients did not meet inclusion/exclusion criteria but randomized (if applicable).

Percentages are to be calculated using the number of randomized patients as the denominator for:

- Patients randomized but not treated. This row is to reflect grouping based on randomization assignment.
- Patients randomized and treated.
- Patients treated differently than randomized. This row is to reflect grouping based on randomization assignment.
- Patients who completed study treatment, patients who discontinued treatment
- Patients who completed study treatment period (defined as completing Week 12 visit), patients who discontinued study treatment period and reason for study treatment period discontinuation, patients who had infusion interruptions and reason.

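### The SAP ties the primary-analysis penalty to stopping study drug instead of dropping out, does not list the change, and leaves withdrawals after the week-8 infusion ambiguous

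*SAP*

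**What the plan says.** Protocol 10.4.3.1 (and the synopsis) sets the trigger by dropout: "For patients who drop out due to lack of efficacy or AEs, each imputed value will be further adjusted by subtracting the mean change" in the same treatment group. Dosing status plays no part.

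SAP 5.7.1 sets it by treatment status. The general text reads "For patients who permanently discontinue treatment due to lack of efficacy, death or AEs, each imputed value obtained through the above method" is adjusted. Step 3 repeats the condition, "For patients who permanently discontinued study treatment due to lack of efficacy, death or AEs, the initially missing and now imputed" scores, and restricts the shift to visits after treatment discontinuation. Step 2 has the same restriction: "The missing data at visits subsequent to treatment discontinuation are to be imputed using the regression method for the monotone pattern". For patients who stop treatment for any other reason, the general text assigns their later missing scores to regression under missing at random (MAR).

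On dosing, the note to protocol Figure 1 says that "study drug will be administered at the day 1 (baseline) visit and at the week 4 and week 8 visits". The SAP disposition section (5.5) has one entry for completing or discontinuing treatment, with no definition. It has a separate entry for "Patients who completed study treatment period (defined as completing Week 12 visit").

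The changed trigger appears neither in Table 1 of the SAP (changes from the protocol) nor in Table 2 (changes from SAP version 1.0).

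**The concern.** Dropping out and stopping drug are different events. Protocol 7.3.2 separates them and asks patients who stop drug to stay for the remaining visits. A patient who has had all three infusions has no dose left to discontinue. If that patient leaves for lack of efficacy, an AE or death before giving a week-12 score, the words of Step 3 do not reach the case. What remains is the general sentence on monotone missing data, which is regression with no adjustment.

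The pattern-mixture adjustment entered the protocol through Amendment 1, on health-authority feedback. The documents do not spell out its purpose. The natural inference is that it stops patients who fail treatment from being credited with the improvement of those who remain. An unlisted change in whom it covers alters the primary analysis. Two programmers could also build different primary datasets from the same text. The supportive averages over weeks 4, 8 and 12 and over weeks 8 and 12 use the same missing-data method (SAP 5.7.1.1).

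**Working it through.** **The plan's own figure.** Protocol 10.2 gives SD 2.3, difference 1.1, 80 per arm, two-sided 0.05, and 15% dropout (6% lack of efficacy or AE, 9% other). Completers: 80 × 0.85 = 68 per arm. SE = 2.3 × √(2/68) = 0.394. Power = Φ(1.1/0.394 − 1.96) = 79.6% (79.1% by noncentral t). The stated power of about 80% reproduces and is not in question here.

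**Who is reached, when the week-12 score is missing:**

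| Patient | Protocol 10.4.3.1 | SAP 5.7.1 |
|---|---|---|
| Stops drug and leaves, both for lack of efficacy or AE | Adjusted | Adjusted |
| All three infusions, then leaves before week 12 for lack of efficacy or AE | Adjusted | Literal reading: not adjusted. Broad reading: adjusted |
| Stops drug for another reason, stays, later leaves before week 12 for lack of efficacy or AE | Adjusted | MAR, not adjusted (explicit) |

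**Which late leavers lack a week-12 score.** Nominally the last infusion is day 57 and week 12 is day 85, a gap of 28 days. The early-termination visit includes WOMAC, and SAP 6.4 maps such visits on days 72–99 to week 12. Protocol 8.1.3 also asks patients withdrawn before week 12 to return at week 12. The exposed group is therefore mainly those who leave on about days 58–71 (14 days) and do not return, plus later leavers with neither an early-termination WOMAC from day 72 nor a week-12 return.

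**Size per patient.** Step 3 subtracts the arm's mean change. Improvement is a negative change, so the subtraction raises the score. A patient who escapes Step 3 keeps a score that is better by the arm's whole mean change, before truncation to 0–10.

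**Equal dropout across arms.** Let f be the share of the 6% who leave late with no week-12 score. The documents do not give f, so it is assumed. Expected difference = 1.1 × [1 − 0.06 × (1 − f)]. With everyone penalised (f = 0), it is 1.1 × 0.94 = 1.034.

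| f | Patients per arm (4.8 × f) | Expected difference | Overstatement |
|---|---|---|---|
| 1/6 (14 of 84 days, uniform dropout) | 0.8 | 1.045 | 0.011 |
| 1/3 (28 of 84 days) | 1.6 | 1.056 | 0.022 |
| 1/2 | 2.4 | 1.067 | 0.033 |
| 1 (ceiling) | 4.8 | 1.100 | 0.066 |

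Against the SE of 0.394, an overstatement of 0.022 is about 6% of one standard error, and 0.066 is about 17%.

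**Unequal dropout.** Assume mean improvements of 2.0 on placebo and 3.1 on active. Shift = p(active) × 3.1 − p(placebo) × 2.0, where p is the proportion of the arm that escapes Step 3.

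- Total lack-of-efficacy or AE dropout 8% active, 4% placebo, f = 1/3: (0.08 × 3.1 − 0.04 × 2.0)/3 = +0.056.
- 4% active, 8% placebo, f = 1/3: (0.04 × 3.1 − 0.08 × 2.0)/3 = −0.012.
- Extreme case, 5% late on active and none on placebo: 0.05 × 3.1 = +0.155. The reverse gives −0.05 × 2.0 = −0.10.

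**Second route.** The documents give no rate for patients who stop drug for another reason and later withdraw for lack of efficacy or an AE, so it cannot be sized. Each such patient shifts by the same amount, the arm's mean change.

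**The case against.** The strongest reply is that the SAP never says late leavers escape the penalty. Its explicit MAR sentence covers only discontinuation for other reasons. Several places treat treatment as lasting to week 12: the Step 3 reference mean uses patients on treatment with data at each time point, the Treatment Period runs to last dose plus 28 days (SAP 5), and week 12 is the end-of-treatment visit. The literal reading also leaves Step 2 silent on these patients, although the procedure must produce 50 complete datasets. All of this stands, and it is why the three-infusion case is called ambiguous. None of it defines discontinuing treatment, and none of it touches the second route, where the text is explicit.

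A reader might infer that the SAP drops the penalty for everyone who leaves in the final four weeks. The documents do not support that. It depends on one reading of an undefined term, and early-termination scores from day 72 and requested week-12 returns supply observed values for many such patients.

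It can also be said that Step 2 conditions on all earlier scores, so a late leaver's imputed value already reflects a poor course. That makes the unadjusted value less optimistic, but the gap between adjusting and not adjusting remains the arm's mean change, apart from truncation.

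**Conclusion.** The SAP changed the penalty trigger without listing the change. For patients who stop drug for another reason and later withdraw for lack of efficacy or an AE, the SAP contradicts the protocol. For patients who leave after the third infusion, the rule is at least ambiguous.

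Relative to the protocol's rule, the expected overstatement is about 0.01 to 0.03 points for f between 1/6 and 1/2, and at most 0.066. This rests on the planned 6% being equal across arms, a true difference of 1.1, and the literal reading. It excludes the second route.

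A reader might take the 0.155 case as the likely bias. It needs nearly the whole planned 6% to fall late in one arm and none in the other, and nothing in the documents suggests that. Nor do the documents suggest that the conclusion would change: SAP 1.2.4.2 reports no significant week-12 difference for either dose, and with equal dropout the bias runs in favour of the drug. The point is about an accurate and reproducible primary analysis, not about rescuing or overturning the result.

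**What to change.** In SAP 5.7.1:

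- Define the Step 3 group as patients with a missing score up to week 12 whose recorded reason for stopping study drug, or for leaving the study or treatment period before the week-12 visit, is lack of efficacy, AE or death, whatever the number of infusions received. This keeps the SAP's present reach and restores the protocol's. It is somewhat broader than the protocol's dropout wording alone, so say so.
- Reword Step 2 to cover all remaining monotone missing data up to week 12.
- List the change of trigger among the modifications from the protocol.
- Check whether any patient is reclassified. If so, report the re-run beside the existing week-12 result, labelled as a correction made after unblinding.

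The cost is a few sentences, one table entry and at most one re-run. The reasons for leaving the treatment period and the study are already collected for the disposition summary in SAP 5.5.

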#### 10.4.3.2. Secondary Efficacy Analysis

The continuous secondary endpoints will be analyzed similarly as specified in Section 10.4.3.1.

For the analyses of categorical secondary endpoints, the Cochran-Mantel-Haenszel test stratified by the K-L category (2-3 vs 4) will be used with missing data considered as non-response. The continuous secondary endpoints will be analyzed similarly as specified in Section 10.4.3.1.

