**Table 1: SAP Version 1 Modifications from Final Protocol Amendment PA1**

Item no.	Issue Addressed	Protocol Amendment 1 Text	SAP V1 Clarification or Addition
1.	In order to be in compliance with SOP-CTM2620 Protocol Deviations Management, the terminology for PD classification changed, from minor and major , to minor and important .		
2.	The Per Protocol analysis set definition is clarified, as not all major/important PDs are to produce exclusions from PP.	The per protocol set (PPS) will include all randomized patients who complete the 12-week treatment period and who do not have major protocol deviations through week 12. The PPS will be used for sensitivity analyses for the primary and selected secondary endpoints.	The per protocol set (PPS) includes all randomized patients who complete the 12-week treatment period and who do not have relevant protocol deviations (PDs) through week 12. The PPS is to be used for sensitivity analyses for the primary and selected secondary endpoints. The relevant PDs are defined as a subset of the important PDs in Appendix 11.4.
3.	The statistical model used for categorical analyses: randomization strata is clarified as only the KL-score to be used besides baseline endpoint score.	The regression model will adjust for treatment, randomization strata, and baseline score.	“... is to be analyzed using a MMRM with terms for baseline WOMAC Pain subscale score, randomization strata (K-L category [2 to 3, or 4]), treatment, visit, and treatment-by-visit interaction as fixed effects.”

Item no.	Issue Addressed	Protocol Amendment 1 Text	SAP V1 Clarification or Addition

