### **5.7.2. Analysis of Secondary and Exploratory Efficacy Variables**

Analyses of continuous variables in secondary (Section 4.4.2) and exploratory (Section 4.4.3) endpoints are to use the same analysis method as the primary efficacy variables.

Analysis of categorical variables in secondary endpoints (Section 4.4.2) is to use the Cochran-Mantel-Haenszel approach stratified by the K-L category (2-3 vs 4 for index knee at screening) with missing data considered as non-response.

Exploratory endpoints for MOTICON (Section 4.9) will be addressed in a separate SAP.

Plots of mean values and change from baseline in PGA, WOMAC subscale and total score by Visit: Least Squares Mean (+/- SE) will be presented.

Cumulative distribution of percent change from baseline to Week 12 in the WOMAC pain and physical function scores will be presented by treatment group. The cumulative distribution plot displays a continuous plot of the percent change from baseline on the X-axis and the percent of patients experiencing that change on the Y-axis.

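### SAP 5.7.1 writes only baseline WOMAC pain into the model shared by all continuous endpoints, against its own Table 1 and the protocol; read literally, function and PGA lose precision

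*SAP*

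**What the plan says.** SAP 5.7.1 lists H1–H6 (pain, physical function and PGA, each for two doses) and then states: "The above primary and secondary efficacy variables are to be analyzed using a multiple imputation approach with a mixed-effect model for repeated measures (MMRM"). One model follows: "Each imputed data set is to be analyzed using a MMRM with terms for baseline WOMAC Pain subscale score", plus K-L category, treatment, visit and treatment by visit. No other baseline outcome term appears. SAP 5.7.2 says that the continuous secondary and exploratory "endpoints are to use the same analysis method as the primary efficacy variables", again naming no other baseline; this brings in WOMAC stiffness and WOMAC total.

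Other text points elsewhere:

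- SAP Table 1, item 3, comments on this same model sentence: "randomization strata is clarified as only the KL-score to be used besides baseline endpoint score".
- Protocol 10.4.3.1 describes an ANCOVA "model which will include treatment, randomization strata, and baseline score as covariate", without naming pain.
- Protocol 10.4.3.2: "The continuous secondary endpoints will be analyzed similarly as specified in Section 10.4.3.1".
- The imputation steps in SAP 5.7.1 refer generically to the baseline of the WOMAC subscale, not to pain. They do not mention PGA.

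**The concern.** Two programmers could fit different models in good faith. One follows the model sentence in 5.7.1 and adjusts function and PGA for baseline pain. The other follows Table 1 and the protocol and adjusts each endpoint for its own baseline. They would report different estimates, standard errors and p-values.

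The literal version is also the weaker analysis. When change from baseline is modelled without its own baseline, variation due to regression to the mean stays in the residual unless the substitute covariate carries it. Chance imbalance between arms in baseline function or PGA is then corrected only as far as baseline pain tracks it. Four of the six ordered hypotheses (H3–H6) concern endpoints other than pain.

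**Working it through.** **The plan's own figure.** SAP 2.2 gives SD 2.3, difference 1.1, 80 per arm, 15% dropout, two-sided 0.05 and about 80% power for WOMAC pain.

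- Evaluable per arm: 80 × 0.85 = 68.
- SE = 2.3 × √(2/68) = 0.394; 1.1/0.394 = 2.79.
- Power = Φ(2.79 − 1.96) = 79.6% (79.1% with the t distribution).

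The stated figure reproduces. It covers pain only; no power or precision is given for function or PGA.

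**Formula for the loss.** Take a week-12 linear model of change, Y12 − Y0, with each variable scaled to variance 1 at both times. Let r = corr(Y0, Y12) for the endpoint, c = corr(baseline pain, Y0), and assume corr(baseline pain, Y12) = c × r.

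- Residual variance given own baseline: 1 − r².
- Residual variance given baseline pain: 2(1 − r) − c²(1 − r)².
- Variance ratio, pain over own: V = [2 − c²(1 − r)]/(1 + r).
- Power, where own-baseline adjustment would give 80%: Φ(2.80/√V − 1.96).

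**Inputs.** The documents give neither r nor c, so these are assumptions: function r 0.4–0.6 and c 0.80–0.85; PGA r 0.3–0.5 and c 0.4–0.5.

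| Endpoint | r | c | V | SE ratio √V | Power |
|---|---|---|---|---|---|
| Function, larger loss | 0.4 | 0.80 | (2 − 0.384)/1.4 = 1.154 | 1.074 | 74% |
| Function, smaller loss | 0.6 | 0.85 | (2 − 0.289)/1.6 = 1.069 | 1.034 | 77% |
| PGA, larger loss | 0.3 | 0.4 | (2 − 0.112)/1.3 = 1.452 | 1.205 | 64% |
| PGA, smaller loss | 0.5 | 0.5 | (2 − 0.125)/1.5 = 1.250 | 1.118 | 71% |

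V is also the factor by which the sample would have to grow to recover the precision.

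**Sensitivity to the third correlation.** At r = 0.4 and c = 0.80, c × r is 0.32. If corr(baseline pain, Y12) were 0.40 instead, the pain-adjusted residual would be 1.2 − (0.40 − 0.80)² = 1.04 against 0.84, so V = 1.24 rather than 1.15.

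**Simulation check** (68 per arm, 4,000 replicates, effect set for 79.6% power with own baseline):

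- r 0.5, c 0.8: SE ratio 1.06; power 78.6% with own baseline, 73.7% with pain.
- r 0.4, c 0.5: SE ratio 1.15; power 77.9% with own baseline, 67.0% with pain.
- Rejection rate under no effect, both models: 4.2–5.0%.

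These calculations leave out the earlier visits and the imputation step, so they show the order of magnitude only.

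**The case against.** The best defence is that nobody meant to omit the own baseline. Section 5.7.1 is headed as the primary analysis and worded for pain. Applying the same method to another endpoint naturally means substituting that endpoint's baseline, and Table 1 and the protocol both say as much. Other wording in 5.7.1 has to be adapted in the same way: imputed values are truncated to 0–10, whereas PGA runs from 1 to 5. This stands as evidence of intent, so a reader who infers that the plan settled on leaving out the own baseline goes further than the documents allow.

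It does not remove the inconsistency. Table 1 item 3 is a modifications table whose SAP column repeats the pain term, and its issue column refers to categorical analyses. It cannot override the operative sentence, which Table 2 does not list as changed in version 2.0. The same section also uses generic subscale wording in the imputation steps and names pain only in the analysis model.

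A reader might also infer that the imputation step already uses each endpoint's own baseline. The generic wording can be read that way for the WOMAC subscales, but for PGA no baseline covariate is named.

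Finally, the loss for function is small if baseline pain and function correlate highly, and pain then absorbs part of any chance imbalance. That is right.

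**Conclusion.** The point holds as an inconsistency in a pre-specified covariate whose literal reading is the less precise one. Under the assumed correlations, intervals would be about 3–7% wider for function and 12–21% wider for PGA (from √V). The size rests entirely on those assumptions; no figure is offered for stiffness or total.

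Two stronger inferences are not supported. First, bias or an inflated type I error: randomisation keeps the pain-adjusted contrast valid, and the simulated error rate did not exceed nominal. Second, a changed trial conclusion: SAP 1.2.4.2 reports no significant week-12 difference in pain for either dose, so the ordered procedure stops at H1 and H3–H6 are not formally tested. What remains affected is the reported estimates, standard errors and intervals for function, PGA, stiffness and total. These still matter, because their width determines how large an effect a negative result can exclude.

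**What to change.** - In the SAP 5.7.1 model sentence, replace the baseline pain term with *the baseline value of the endpoint being analysed*, applying to every continuous endpoint in 4.4.2.
- In the imputation steps, state that the baseline covariate is that of the score being imputed, and name PGA explicitly.
- In the study report, state which baseline covariate was used for each endpoint in the week-12 analysis. Because SAP version 2.0 follows review of the unblinded week-12 results, label any change of covariate as made after unblinding.

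No new data are needed: the schedule of events collects the full WOMAC survey and PGA at the baseline visit. If own baselines were already used, the cost is a few words. If baseline pain was used, the models for function, PGA, stiffness and total must be rerun, with the disclosure above.
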